#### Intervention Delivery

This pilot study will use text messages to deliver four behavioral change techniques identified in Michie et al.’s (2011) paper which identified those BCTs associated with influencing change in physical activity behavior. These BCTs were updated to align with current BCT definitions using Michie et al.’s (2013) Taxonomy of Behavioral Change Techniques. A list of BCTs is provided as an appendix to this protocol. Participants will also receive **bi-weekly surveys** to assess their satisfaction with the given BCT and walking self-efficacy. BCTs will be provided to participants in a randomized crossover design with each BCT delivered individually in one of four 2-week blocks. The order in which participants receive BCTs will be randomized with the randomization order determined by the study

statistician. Prior to BCT delivery (i.e. every two weeks) participants will be sent information/BCT descriptions the day before they start their new BCT so that they understand the differences between the four BCTs for their personalized trial. For instance, BCT descriptions may include:

BCT Name	Definition	Sample Text Message Prompt
Goal Setting Behavior	Set or agree on a goal defined in terms of behavior to be achieved	Set the goal of being more active today. Record your goal
Action Planning	Prompt detailed planning of performance of behavior (must include a setting frequency, duration, and intensity)	“It’s Tuesday. Walk 2,000 steps from 10am -11am this morning.”
Self-Monitoring of Behavior	Establish a method for person to monitor and record their number of active periods based on their Fitbit	“It’s time to check your FitBit dashboard and view how active you have been today.”
Feedback on Behavior	Monitor and provide informative or evaluative feedback on performance of the behavior (e.g. form, frequency, duration, intensity)	“You met your goal yesterday. You walked 2,000 steps more than baseline.”

Participants may receive additional text messages to those outlined above with important reminders to sync their data as needed.

Upon completion, participants in the personalized trials phase will receive an individual report that demonstrates their walking responses in relation to their assigned BCTs and a satisfaction survey to obtain feedback about their personalized trials experience.

## 12. STATISTICAL ANALYSIS

- *Describe how your data will be used to test the hypotheses.*
- *State clearly what variables will be tested and what statistical tests will be used.*
- *Include sample size calculations.*
- *If this is a pilot study, state which variables will be examined for hypothesis generation in later studies.*

The sample size of 60 participants for testing the Personalized Trial was chosen to have a sufficient number of participants to obtain a preliminary assessment of the feasibility of Personalized Trials of the four behavioral change techniques as

compared to baseline. The numbers of prompts and reports were based on expert recommendations and estimations about maximal duration of the trial to maintain patient engagement. Data will be reported transparently so that individual level heterogeneity can be assessed.

Means and standard deviations of step scores for baseline versus behavioral change strategy treatment period will be visualized using a column graph. The statistical significance of differences will be adjusted for time interval. The effects of treatment on number of steps will be assessed using generalized estimating equations (GEE) with an unstructured variance-covariance matrix for measures on the same day. This model accounts for possible autocorrelation and linear trends between steps across time.

Data from the four small sample preliminary phases will be considered as descriptive data/information and will not be statistically analyzed.

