## 9. STUDY TIMELINES

- *Describe the duration of an individuals participation in the study*
- *Describe the duration anticipated to enroll all study subjects*
- *The estimated date of study completion*

The initial phases of study participation will involve either a single session via a virtual interaction (electronic meeting, 1:1 interview or electronic correspondence) or remote evaluation of study message content and frequency over the course of five days. The last study phase will involve a total of 10 weeks of study participation: activity tracking using a Fitbit activity monitor for 10 weeks, and

responding to behavior change strategy prompts and surveys delivered via text message to a secure link for 8 weeks. At the end of the 10 week intervention period, a report containing the individual's responsiveness to each BCT will be sent to the participant, along with a satisfaction survey.

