In the four preliminary phases (with up to 10 participants each in phase 1,3, 4 and up to 30 participants in Phase 2), virtual focus groups and/or 1:1 discussions will be held to answer questions and elicit feedback about the comprehensibility of behavior change strategy descriptions, special study website content and videos, the ability to receive “sample” study messages in home and work settings, the virtual informed consent process, and study tools with attention toward for clarity and ease of use.

Potential participants for the Personalized Trial Participants will be sent a secure message with the start date of their baseline period, as well as a review of what to expect during onboarding to the study. They will be mailed an initial study kit including a Fitbit device. A PDF copy of their electronically signed consent form will be made available to all participants via N1Thrive/REDCap secure messaging. Potential participants will be asked to download the Fitbit app to their smart phone. No more than 20 participants will be permitted to begin on the same day.

The baseline period will take place over the course of two weeks. During the baseline period, potential participants will be asked to wear their Fitbit for 10 ours per day and also while they are sleeping, as tolerated and to acknowledge receipt of a daily text message that is not an activity prompt. Baseline participants will be instructed to sync their Fitbit device by opening the Fitbit app on their phone at least every two days.

Individual adherence to Fitbit wear and to survey responses will be assessed in order to determine which individuals progress to intervention. Adherence to Fitbit wear will be defined as recorded activity of greater than 10 hours a day. Text message adherence will be defined as responding to a given text message. Baseline participants that do not achieve at least 80% adherence of Fitbit wear and text responsiveness the baseline period will be withdrawn from the study. Those that maintain at least 80% adherence will be randomized to one of their selected behavior change techniques to begin their pilot personalized trial. Participants who are randomized to receive intervention sequences will receive email confirmation including their protocol timeline. Enrollment will continue until up to 60 participants have been randomized.

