## 16. WITHDRAWAL OF SUBJECTS

- *Describe anticipated circumstances under which subjects will be withdrawn from the research without their consent*
- *Describe procedures for orderly termination*
- *Describe procedures that will be followed when subjects withdraw from the research, including partial withdrawal from procedures with continued data collection.*

Concern for withdrawal of study participants is likely only relevant to participants engaged in the 10-week personalized trial. Circumstances under which participants will be withdrawn from the research without their consent include failure to maintain protocol adherence, repeated failure to respond to text prompts or self-reported adverse side effects of increased walking. A participant will not be randomized to receive the (8-week) intervention protocol until he/she has demonstrated at least 80% adherence to Fitbit monitoring (activity recorded at least 10 hours/day during the two-week baseline period of the personalized trial).

Participants will be notified in the informed consent of the possibility of being removed from the study before the 8-week intervention period due to adherence issues.

Participants who fail to maintain protocol adherence or who deviate from the protocol will be contacted by a member of the study team with a reminder of the study protocol, and warning that this may impact their continued study eligibility. Once a protocol deviation has been repeatedly recorded, the Principal Investigator will determine the participant's continued eligibility in the study, with consultation of the safety monitor if needed. If it is determined that the participant will be withdrawn from the study, the participant will be notified by the research team via email and phone call. The participant will stop receiving notifications and BCT prompts, and will be sent instructions to un-link their Fitbit device. Participants who are withdrawn due to low adherence during the intervention portion will be able to keep their Fitbit.

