Should a participant choose to withdraw from research, they will be instructed to email the study email address ([[contact]](mailto:[contact])), an e-mail account monitored by IRB-approved members of the research team. Participants will be contacted by a member of the research team confirming their study withdrawal, and to answer any questions they may have. The participant will stop receiving notification and survey prompts, and will be sent instructions to un-link their Fitbit device. Data collection will stop the business day the letter or email is received. All data up until the receipt date of the letter will be included in the research study.

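### Does Section 12 need a rule for which Fitbit days enter the comparison of steps at baseline and under each behaviour change technique?

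*Combined protocol and SAP*

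**What the plan says.** Section 12 gives two step analyses. One is descriptive: "Means and standard deviations of step scores for baseline versus behavioral change strategy treatment period will be visualized using a column graph". The other is the model: "The effects of treatment on number of steps will be assessed using generalized estimating equations (GEE". Neither comes with a minimum wear time, a definition of a valid day, or handling of partial or unsynced days.

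Wear is addressed in Section 11. The instruction is tied to the time before randomisation: "During the baseline period, potential participants will be asked to wear their Fitbit for 10 ours per day and also while they are sleeping". The definition follows: "Adherence to Fitbit wear will be defined as recorded activity of greater than 10 hours a day". It is used for a gate that begins "Baseline participants that do not achieve at least 80% adherence of Fitbit wear" and ends in withdrawal before randomisation. Section 16 restates the gate as "activity recorded at least 10 hours/day during the two-week baseline period".

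For the eight weeks on the behaviour change techniques (BCTs), Section 9 says tracking continues, Section 11 allows sync reminders, and Section 16 provides reminders and case-by-case withdrawal for poor adherence. No hours or percentage are attached to those weeks. For people who choose to leave, Section 16 says "All data up until the receipt date of the letter will be included in the research study".

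**The concern.** The comparison is against baseline, and people enter the trial only if they wore the device well during baseline. Two weeks is a noisy measure of a person's wear habit, so those who pass will on average wear the device somewhat less afterwards. This is regression to the mean and needs no change in behaviour. Unworn hours record no steps, so a fall in wear looks like a fall in walking. Section 12 adjusts for time interval and linear trend but has no wear term.

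Two analysts could also make different choices, such as all days or only days reaching 10 hours, and obtain different pooled effects. The same daily data feed the individual report, in which each person's "responsiveness to each BCT will be sent to the participant, along with a satisfaction survey". Finally, the wear definition does not say whether hours recorded asleep count, and Sections 11 and 16 word the 10-hour threshold differently.

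**Working it through.** **From the documents.** The plan states no figure on this point to reproduce. The gate is 80% of 14 days: 0.8 × 14 = 11.2, so 12 days must pass (11/14 = 78.6% fails, 12/14 = 85.7% passes). Section 8 allows up to 180 people in all, up to 60 of them in the preliminary phases. That leaves 180 - 60 = 120 places from which up to 60 are randomised.

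**Assumed, because the documents give no step or wear data.** True steps are constant at 7,000 a day. A low-wear day loses 50% of its steps (range 25% to 75%), and a 10-hour day loses none. Each person's chance of a 10-hour day follows a beta distribution (a, b) with mean 0.80 (range 0.75 to 0.90) and concentration a + b = 10 (range 5 to 20).

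**Selection effect.** Let k be the number of 10-hour days in 14, which is beta-binomial.
- Baseline share among those who pass = E[k/14 | k ≥ 12].
- Later share = E[(a + k)/(a + b + 14) | k ≥ 12].
- Central case (a = 8, b = 2): 51.7% pass, baseline share 0.923, later share 0.872, gap 0.051.

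**Apparent change when nobody changes their walking.**
- All days in both periods: -7,000 × 0.0511 × 0.5 = -179 steps a day.
- 10-hour days in both periods: 0, by construction.
- 10-hour days at baseline but all days under the BCTs: -7,000 × (1 - 0.8716) × 0.5, or about -450. No section states this mixed rule. Section 11 uses the 10-hour definition to select people, not days.

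**Which cases fit the enrolment ceiling.** Baseline starters needed = 60 / pass rate.
- Mean 0.75: 135 to 172 starters, above 120. The most extreme all-days result (-470, at 75% loss) needs 172.
- Mean 0.80: concentration 5 needs 108 starters (-127 steps), 10 needs 116 (-179), and 20 needs 122 (-229, just over the ceiling).
- Mean 0.85 to 0.90: 74 to 92 starters, -57 to -151 steps.

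At 50% loss, the cases that fit run from -57 to -179. Varying the loss from 25% to 75% widens this to between -29 and -268.

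**Scale.** For one 14-day BCT block against the 14-day baseline in 60 people, SE = sqrt(SD² × (2/14) / 60).
- Daily SD 3,000 (assumed), independent days: 146. With a between-person effect SD of 1,000: 195.
- With autocorrelated days, SE = sqrt(2 × SD² × v / 60), where v = (1/14²) × Σ ρ^|i-j|. For ρ = 0.3, v = 0.126 and SE = 195. For ρ = 0.5, v = 0.194 and SE = 241.
- Hence 179/146 = 1.2, 179/195 = 0.9 and 179/241 = 0.7 SE.

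The target, 2,000 steps on 5 days a week, averages 2,000 × 5/7 = 1,429 steps a day, so 179 is about an eighth of it.

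**Between BCTs.** The baseline term cancels. What remains is any wear difference between blocks: a 5-point difference is worth 7,000 × 0.05 × 0.5 = 175 steps a day (88 to 262 over the loss range). The documents give no reason to expect a difference of that size.

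**The case for a change.** The strongest case for acting is that the selection effect has a known direction, that all-days and 10-hour-days analyses can differ by more than selection alone implies if wear also decays, and that a few sentences would settle the matter. If low-wear days rose from 10% to 30% (assumed) and recorded 25% to 50% of true steps, the all-days shift would be 5,000 × 0.20 × 0.50 = 500 to 10,000 × 0.20 × 0.75 = 1,500 steps a day, which is comparable with the target.

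What stands is that Section 12 is silent, and that an analyst who ignored wear could understate the effect. What does not stand is that this calls for a different plan:

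- Neither day set is clearly better. All days carry wear differences into the step estimate. Restricting to 10-hour days conditions on behaviour after randomisation that a BCT may itself change, since the Self-Monitoring sample prompt sends people to their Fitbit dashboard.
- Prompts could also raise wear, so the net direction is not fixed. Section 16's reminders and withdrawals would limit a fall.
- The zero for 10-hour days depends on such days losing no steps. If steps fall evenly over 16 waking hours, a day with 10 waking hours of wear records only 10/16 = 62.5% of them, so the restriction is not a clean cure.
- The Section 16 sentence on withdrawal covers people who choose to leave. It does not govern wear and affects at most one partial day for each of them.
- The two threshold wordings differ only at exactly 10 hours. The instruction in Section 11 reads naturally as daytime wear plus sleep, so a day that passes mainly on sleep hours is an extreme case.

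**Conclusion.** This is a gap that analysts fill sensibly. The plan does not state a day rule that would mislead. It states none, and the ordinary choice is one rule applied alike to baseline and all BCT blocks. Under that choice, selection on baseline wear costs nothing (10-hour days, on the simple model) or about 57 to 179 steps a day (all days), at most about one standard error for a single BCT against baseline. These sizes rest entirely on the assumed step level, step loss, wear distribution and daily SD. Larger figures need either a mixed rule that no section contains, wear so poor that 60 people could not be randomised within the enrolment ceiling, or an assumed decay in wear for which the documents give no evidence.

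Section 10 makes pooled efficacy secondary to acceptability, scalability and satisfaction, and Section 12 sets the sample size on feasibility grounds. Section 14 lists daily steps, heart rate and sleep duration among the Fitbit data that may be collected, so wear can be examined and either day set analysed without new data. The difference in the 10-hour wording is a clerical slip. No change to the plan is needed.

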## 2. BRIEF SUMMARY OF RESEARCH

- *The summary should be written in language intelligible to a moderately educated, non-scientific layperson.*
- *It should contain a clear statement of the rationale and hypothesis of your study, a concise description of the methodology, with an emphasis on what will happen to the subjects, and a discussion of the results.*
- *This section should be ½ page*

The purpose of this pilot study is to determine the feasibility of using N-of-1 methods in a virtual research study with Northwell employees aged 45-75 years old to increase low-intensity walking by 2,000 steps per day/5 days per week using four behavior change techniques, provided in random order, and shown to have been effective in changing physical activity. This pilot will help determine if a Personalized Trial design can have widespread use in future research and clinical practice.

In preliminary phases, participants, via secure surveys delivered electronically and/or via interactive Microsoft Teams meeting(s) for focus groups and/or 1:1 interviews, will finalize the content and design features used to deliver the study messaging.

Up to 60 participants will provide feedback on key aspects of study design, including BCT description, materials and electronic delivery methods, such as text messaging and email receipt. Focus group techniques, interviews and/or surveys may be used to elicit feedback concerning the clarity of instructions and convenience of messaging. At least 10 of these participants will engage with study materials and procedures as “mock participants,” interacting remotely from their home or office, and providing feedback about the ease and acceptability of study procedures to further refine study materials and procedures. In the final, intervention phase of the study, up to 60 participants will be randomized to the 10 week personalized trial assessing the impact of 4 BCTs assigned in random order on their walking behavior.

Participants will be sent a Fitbit physical activity monitor that will track the number of steps taken per day. Depending upon the BCT assigned, the participant will

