## 8. NUMBER OF SUBJECTS

- *Indicate the total number of subjects to be accrued locally. If applicable, distinguish between the number of subjects who are expected to be pre-screened, enrolled (consent obtained), randomized and complete the research procedures.*
- *If your study includes different cohorts, include the total number of subjects in each cohort.*
- *If this is multisite study, include total number of subjects across all sites.*

We expect to pre-screen and enroll up to 180 potential participants in this study. Up to 60 participants will be recruited across the four preliminary (brief duration) phases. Up to 60 participants will be randomized to the 10 week personalized trial, first undergoing a 2 week baseline monitoring of their walking behavior, followed by 8 weeks of monitoring their walking in response to each of the four behavioral change techniques (2 weeks per technique).

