#### Fitbit

This pilot study uses Fitbit devices to remotely monitor participant activity and sleep. All enrolled participants will be provided with a study account that has been created by the research team with no identifying information to the participant. The email address of the study account contains a unique identifier (e.g. northwellf25). Data collected by the activity monitor may include daily steps, floors climbed, activity intensity, heart rate, sleep duration, and estimated minutes in sleep stages. A file linking the Fitbit identifier to the study participant will be housed in a Northwell-approved drive to store PHI, and be accessible only by members of the study team listed in the IRB application. Coded data from Fitbit will remain stored in a Northwell-approved drive indefinitely, but the file linking the Fitbit identifier to the study participant will be destroyed upon completion of an individual's participation with the study.

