#### Fitabase

The Personalized Trial Study will use Fitabase to retrieve Fitbit data from participant activity tracking devices. Fitabase is a secure, online portal. The Fitbit study account provided to the participants will be linked to an identification number in the Fitabase system (e.g. FLT01). No information that could be used to identify a participant will be stored on Fitabase. Only the research team will have access to data that will be able to connect a research participant to their Fitabase ID. Data collected may include last sync date, battery charge status, daily steps, floors climbed, activity intensity, heart rate, sleep duration, and estimated minutes in sleep stages. Fitabase will stop tracking participant data at the trial end date selected by the research coordinator. As an added measure, participants will be instructed to remove the Fitbit study account from their device if they plan to keep the Fitbit.

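### The GEE in section 12 is said to handle autocorrelation, but its only stated covariance links measures within a single day, and neither the cluster nor the standard-error type is given

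*Combined protocol and SAP*

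**What the plan says.** Section 12 (Statistical Analysis) contains the whole inferential specification. The effect of treatment on steps is to be assessed by "generalized estimating equations (GEE) with an unstructured variance-covariance matrix for measures on the same day". The next sentence reads: "This model accounts for possible autocorrelation and linear trends between steps across time". The only other remark about time is that significance will be adjusted for time interval, a term that is not defined.

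Section 2 describes the outcome as coming from a "Fitbit physical activity monitor that will track the number of steps taken per day". Section 14 agrees, under Fitbit ("Data collected by the activity monitor may include daily steps, floors climbed, activity intensity") and under Fitabase ("Data collected may include last sync date, battery charge status, daily steps").

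On design, section 8 has participants "first undergoing a 2 week baseline monitoring of their walking behavior, followed by 8 weeks" of intervention. In section 11, under Intervention Delivery, "BCTs will be provided to participants in a randomized crossover design with each BCT delivered individually in one of four 2-week blocks". Up to 60 participants are to be randomized.

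Nowhere does the document name the clustering unit, a between-day correlation structure, or whether standard errors are model-based or robust.

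**The concern.** The property claimed for the model does not follow from the model described. A matrix for measures on one day says nothing about how Monday's steps relate to Tuesday's. A time term in the mean could cover the linear trend, but it leaves residual correlation between days untouched.

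The missing details decide whether the inference is valid. In a within-person crossover, two things must be handled:

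- Stable differences between people should cancel from a comparison of techniques. If every participant-day is treated as independent, those differences stay in the residual and the standard error is too large.
- Correlation from day to day, and shared variation within a two-week block, make the daily values less informative than their number suggests. Ignoring this makes the standard error too small.

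Which error dominates depends on variances that the document does not give. This is the only model stated for the pooled efficacy analysis in the third aim (section 4) and the secondary endpoint (section 10).

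**Working it through.** The plan gives no power, SD or correlation, so there is no figure of its own to reproduce.

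**Step 1. What each reading of the covariance supplies.** Days per participant: 14 baseline + 4 x 14 = 70.

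- One daily total per participant: the same-day matrix is 1 x 1, with no correlations.
- Several counts within a day: the matrix has within-day correlations and still none between days.
- Different participants on the same day: nothing within a participant.
- The wording read as same participant, across all days: 70 x 69 / 2 = 2,415 correlations from at most 60 participants. In simulation the 70-day moment matrix had rank 60 with complete data, so it is singular. With 5%, 10% or 20% of days missing, the pairwise matrix had 16 to 32 negative eigenvalues in every one of 300 runs per level, so it was not a valid covariance matrix.

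**Step 2. Size of the error under the literal reading.** Assumed, not from the document: within-person daily SD 3,000; lag-1 correlation ρ of 0, 0.2 or 0.4 (AR(1)); participant-by-period SD σp of 0 or 800; between-person SD σb of 2,500 or 3,500; 60 participants; complete data; no true effect; two-sided 5%.

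For the difference between two techniques:

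- True SE = √{[2σp² + (2 × 3,000²/14) × A] / 60}, where A is the variance inflation from AR(1), averaged over block positions: 1.000, 1.444 and 2.135 for ρ = 0, 0.2 and 0.4.
- Day-level SE = √{(3,000² + σp² + σb²) × 2 / (60 × 14)}.
- True size = 2 × [1 − Φ(1.96 × day-level SE / true SE)].

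Example where the test is too liberal (ρ 0.4, σp 800, σb 2,500):

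- True SE = √[(1,280,000 + 1,285,714 × 2.135)/60] = 259.0.
- Day-level SE = √(15,890,000 × 2/840) = 194.5.
- Ratio 0.75, size 14.1%.

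Example where it is too conservative (ρ 0.2, σp 0, σb 3,500):

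- True SE = √[(1,285,714 × 1.444)/60] = 175.9.
- Day-level SE = √(21,250,000 × 2/840) = 224.9.
- Ratio 1.28, size 1.2%.

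All 12 settings by formula:

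| σp | σb | ρ | True SE | Day-level SE | Ratio | Size |
|---|---|---|---|---|---|---|
| 0 | 2,500 | 0 | 146.4 | 190.6 | 1.30 | 1.1% |
| 0 | 2,500 | 0.2 | 175.9 | 190.6 | 1.08 | 3.4% |
| 0 | 2,500 | 0.4 | 213.9 | 190.6 | 0.89 | 8.1% |
| 0 | 3,500 | 0 | 146.4 | 224.9 | 1.54 | 0.3% |
| 0 | 3,500 | 0.2 | 175.9 | 224.9 | 1.28 | 1.2% |
| 0 | 3,500 | 0.4 | 213.9 | 224.9 | 1.05 | 3.9% |
| 800 | 2,500 | 0 | 206.8 | 194.5 | 0.94 | 6.5% |
| 800 | 2,500 | 0.2 | 228.6 | 194.5 | 0.85 | 9.5% |
| 800 | 2,500 | 0.4 | 259.0 | 194.5 | 0.75 | 14.1% |
| 800 | 3,500 | 0 | 206.8 | 228.3 | 1.10 | 3.0% |
| 800 | 3,500 | 0.2 | 228.6 | 228.3 | 1.00 | 5.0% |
| 800 | 3,500 | 0.4 | 259.0 | 228.3 | 0.88 | 8.4% |

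Six settings fall below 5%, one sits at 5% and five lie above.

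**Step 3. Simulation.** Random block order; mean model with an intercept, four technique indicators and a linear day term; 4,000 trials per setting (Monte Carlo SE 0.34 points at 5%); normal reference, no small-sample correction.

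| Test and data | Day-level clusters | Participant-clustered sandwich |
|---|---|---|
| Technique vs technique, complete data | 0.3%–14.8% (model-based); 0.2%–14.8% (day-level robust) | 5.2%–6.4% |
| Technique vs technique, 20% of days missing at random | 1.1%–12.1% | 4.9%–6.4% |
| Technique vs baseline, complete data | 0.2%–14.6% | 5.2%–6.5% |

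Robust errors at the day level therefore repair nothing; the level of clustering is what matters. In the complete-data technique comparison, the mean sandwich SE was 0.96 to 1.01 times the true SE.

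**The case against.** The strongest reply is that the text never says the participant-day is the cluster. Read that way, the word unstructured would be empty, and the sentence on autocorrelation suggests the authors do not mean to treat days as independent. Participant clusters with sandwich errors are common GEE practice and would make the claim true. This stands as far as it goes: the harm follows only if an analyst implements the wording as written. It does not make the wording correct, because the reader has to supply both details that determine validity.

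Second, an unstructured matrix over the five periods (baseline plus four blocks) would have only 5 x 4 / 2 = 10 correlations, which 60 participants can support, and section 12 does speak of comparing baseline with treatment periods. That is an estimable model, but it is a different one from a matrix for same-day measures.

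Third, section 11 defines wear adherence by hours of recorded activity, so within-day records may exist. Even so, they would add no correlation between days.

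Fourth, the magnitudes rest on assumptions. With no participant-by-period variation the day-level size runs only from 0.3% to 8.1%, and five of those six settings are conservative. The top of the range needs the highest correlation, the period effect and the smaller between-person SD together. The figures therefore show that the direction of error is unknown; they do not show that false positives are likely.

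Finally, feasibility is the primary objective, the sample size was chosen on that ground, and no alpha or power is stated. No confirmatory decision depends on this model.

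**Conclusion.** The concern holds. Section 12 claims a property that its stated covariance cannot deliver, and it omits the cluster and the standard-error type that would deliver it. The mismatch can be read directly from the text and needs no assumptions.

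Its numerical consequence is conditional on two things: the literal participant-day reading, and variances assumed for this review. Under those conditions a nominal 5% test between techniques may run anywhere from well below 1% to about 15%, whereas participant-clustered sandwich errors stay near nominal. This should be fixed before analysis. It does not undermine the trial, because the pooled efficacy analysis is secondary to the feasibility objective.

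**What to change.** In section 12, delete the phrase about same-day measures and specify the model along these lines:

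> GEE on daily steps with the participant as cluster; technique indicators plus a linear day term; an estimable working correlation (for example exchangeable); participant-clustered robust (sandwich) standard errors, which allow for between-day autocorrelation.

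The cluster and the standard-error type are the essential parts. Exchangeable is only an example: with complete data it gives the same estimates as working independence, and with 20% of days missing its true SE was 2% to 12% smaller. A small-sample correction is optional: the uncorrected sandwich gave 5.2% to 6.4% with 60 participants and 5.3% to 7.2% with 40.

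The cost is one or two sentences, with no added data or participants. Relative to day-level clustering, and under the same assumptions, intervals for technique comparisons would be between 144.2/224.4 = 0.64 and 255.4/194.3 = 1.31 times as wide (mean sandwich SE over mean day-level SE), so in some settings an apparently significant contrast would be lost. If participant clustering with sandwich errors is already what the analysts intend, the results would change little or not at all.
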